## 6.4 Withdrawal of individual subjects

Subjects can leave the study at any time for any reason if they wish to do so without any consequences. The investigator can decide to withdraw a subject from the study for urgent medical reasons.

## 6.5 Replacement of individual subjects after withdrawal

Our sample size calculations accounted for some loss to follow-up, and subjects who withdraw from the study will not be replaced.

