#### 4.4 Sample size calculation

Primary outcome is the time to recurrence measured at two years of prospective follow-up. We will perform a superiority trial. Based on previous literature, we expect 20% recurrence in 2-year with wait-and-see policy (based on a mix of patients with a first and recurrent episode of aSBO) and a 10% recurrence rate after intervention, resulting in a hazard ratio (HR) of approximately 0.47.

We estimated that if 378 patients were randomly assigned in a 1:1 ratio (i.e., 189 per group) to the intervention group or the control group, our study would have 80% power to detect an HR for recurrence of adhesive small bowel obstruction of approximately 0.47 at a two-sided  $\alpha$  level of 0.05. After rounding the total number of patients up, we aim to include a total of 380 patients. Analysis will be performed by intention to treat basis, using survival analysis. We will use cox regression to be able to apply multivariable analysis to account for covariates such as previous episodes of ASBO.

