## Surgery

Patient randomized to the intervention will undergo surgery within 6 weeks following inclusion. Surgery will be performed in accordance to the description of the intervention in chapter 5 of the protocol. Peri-operative care will be performed according to local protocols for elective laparoscopic surgery in the operative centres. Based on previous experiences we expected adhesiolysis to be performed laparoscopically in 70-80% of patients. Average hospital stay following laparoscopic adhesiolysis is 2 days. In converted and open surgery cases, the average stay is 5 days. Operatively treated patients will have a single outpatient visit to evaluate the recovery at 6 weeks post- surgery, or more frequent if a complication has occurred (as appropriate in the care for that complication). No specific follow-up is performed after this single post-operative outpatient visit.

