## 6.6 Follow-up of subjects withdrawn from treatment

Patients withdrawing from the study who randomized to the control arm, or prior the intervention, do not require specific follow-up. Patients withdrawing after the intervention will receive appropriate surgical care. This includes a single outpatient clinic to evaluate recovery at 6 weeks post-operative, as well as care for possible complications of surgery. After full recovery from surgery no specific follow-up is required.

Patient who refrain from surgery after randomization or cross-over from wait-and-see to surgery but do not withdraw from the study as a whole, will be followed according to the study procedures as described above and analyzed based on intention-to-treat.

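### Section 6.5 says the sample size allowed for loss to follow-up, but the calculation in section 4.4 shows no such allowance: 380 is 378 rounded up, and 378 is essentially the no-loss number

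*Protocol*

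**What the plan says.** Section 4.4 sets the design values. For the control arm, "we expect 20% recurrence in 2-year with wait-and-see policy"; for the other arm, "a 10% recurrence rate after intervention, resulting in a hazard ratio (HR) of approximately 0.47". With 1:1 allocation, two-sided alpha 0.05 and 80% power it arrives at 378 patients, 189 per group. The last step is: "After rounding the total number of patients up, we aim to include a total of 380 patients". No loss rate and no division by a retention fraction appear there.

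Section 6.5 then says: "Our sample size calculations accounted for some loss to follow-up, and subjects who withdraw from the study will not be replaced".

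Three other places bear on the point.
- Section 6.1.1 expects little loss of data over two years but gives no figure.
- Section 8 keeps lost patients in the survival analysis until the moment of loss.
- Under Surgery in section 6.3, "Patient randomized to the intervention will undergo surgery within 6 weeks following inclusion", and section 6.6 keeps in the intention-to-treat analysis any "Patient who refrain from surgery after randomization or cross-over from wait-and-see to surgery but do not withdraw from the study as a whole".

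**The concern.** Section 6.5 describes a feature of the calculation that the calculation does not show. If 378 is already the number needed with everyone followed for two years, rounding up by two patients is not a loss allowance, and a reader of 6.5 would think the stated power better protected than it is. An ethics committee or monitoring board would rely on that sentence, and a null result would be read against 80% power.

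A related ambiguity sits in 4.4. The 10% is described as the rate after intervention, while the analysis is by intention to treat. Section 4.4 does not say whether the 10% already includes time waiting for surgery and patients who never have it.

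**Working it through.** **Inputs from section 4.4:** two-year risks 20% and 10%; 1:1 allocation; two-sided alpha 0.05; power 80%; N = 378, rounded to 380. **From section 8:** censoring at the time of loss. **Not given anywhere:** a loss rate, a mean wait for surgery, a non-receipt rate. The values used for these below are assumptions.

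**1. Hazard ratio.** ln(0.90)/ln(0.80) = 0.472, matching the protocol's 0.47.

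**2. Reproducing 378 with no loss.** Schoenfeld events D = 4(1.960 + 0.8416)² / (ln 0.472)² = 55.75. The mean risk is (0.20 + 0.10)/2 = 0.15.
- N = 55.75/0.15 = 372.
- With events rounded up to 56, N = 56/0.15 = 373.3, so 374.

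The stated 378 lies within 2% of this. Other standard no-loss formulas give more than 378 (Freedman about 407, two proportions 398), so they leave no room for an allowance either.

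**3. Slack in 380.** 1 − 372/380 = 2.1%; 1 − 374/380 = 1.6%.

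**4. Power at 380 with no loss.** Events = 380 × 0.15 = 57.0. Power = Φ(½√57.0 × |ln 0.472| − 1.960) = 80.9%.

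**5. Power at 380 with loss (formula).** Two cases bracket the effect of a loss fraction d.
- *Lost patients contribute nothing:* events = 380 × (1 − d) × 0.15.
- *Loss spread over follow-up:* censoring rate g = −ln(1 − d)/2 per year, and the observed risk in an arm with hazard λ is λ/(λ + g) × (1 − exp(−2(λ + g))). At d = 5% the arm risks are 19.5% and 9.8%; at d = 10% they are 19.0% and 9.5%.

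| Assumed loss | Spread: events, power | Contribute nothing: events, power |
|---|---|---|
| 0% | 57.0, 80.9% | 57.0, 80.9% |
| 2% | 56.4, 80.5% | 55.9, 80.1% |
| 5% | 55.6, 79.9% | 54.1, 78.8% |
| 10% | 54.2, 78.9% | 51.3, 76.7% |

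**6. Simulation on one basis.** Log-rank simulation with exponential hazards at N = 380 gives about 79% with no loss. With 5% loss it gives about 78% if loss is uniformly timed and 76.5% if lost patients contribute nothing; with 10% loss, about 76.5% and 74.7%. These values are about two points below the formula throughout, including at zero loss. That gap reflects the approximation and not a missing allowance. Formula and simulated values should not be mixed in one comparison.

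**7. If the 10% applies only to patients promptly operated on.** Let waiting time carry the control hazard (0.1116 per year, against 0.0527 after surgery). A 3-week wait (0.0575 years) gives an arm risk of 1 − exp(−0.1116 × 0.0575 − 0.0527 × 1.9425) = 10.3%. The average hazard ratio is then 0.487 and formula power is 77.9%; simulation gives about 75 to 76%. If 5% are never operated on and carry the 20% risk, the arm risk is 0.95 × 10% + 0.05 × 20% = 10.5%, the hazard ratio 0.497 and formula power 75.8%. This step matters only under that reading of the 10%.

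**The case against.** **The slack could be the allowance.** Section 6.5 claims only some loss and section 6.1.1 expects little. With the hazard ratio as printed (0.47), Schoenfeld needs 55.1 events, or 367 patients, so the slack in 380 could be put at 1 − 367/380 = 3.4%. An allowance of 1 to 2% inside 378 cannot be excluded (374/0.99 = 378). This stands as far as it goes: the two sections are not proved irreconcilable. But no such allowance is stated, and 4.4 attributes its last step to rounding alone.

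**Complete follow-up.** A reader might infer that 80% power holds only if everyone is followed for two years. By formula it does not fail that fast: 2% of patients contributing nothing leaves 80.1%, and 5% spread loss leaves 79.9%.

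**Delay and refusal.** A reader might also fold these into the contradiction, where the drops are larger. Section 6.5 speaks only of loss to follow-up, and 4.4 does not settle that the 10% is an as-treated risk. The protocol's own background reports a reduction of more than 65% after elective adhesiolysis, although over five years and in patients with chronic complaints. A 65% reduction from 20% is 7%. With 10% never operated on, the arm would average 0.9 × 7% + 0.1 × 20% = 8.3%, still below the planned 10%. The design value may therefore already absorb some dilution.

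**A dropped 10% allowance.** Since 378/0.90 = 420, and 140 and 280 in section 8.4 are thirds of 420, one might suspect a lost inflation step. Section 7.4 gives 130 and 260 for the interim safety analyses, which are thirds of 390. Counts that conflict with each other cannot show this.

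**No replacement.** Not replacing withdrawals is sound under intention to treat with or without an allowance, so that rule does not fall.

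**Conclusion.** Section 6.5 is wrong as written, in the sense that the protocol's only calculation does not support it. The stated inputs need about 372 to 374 patients with no loss, 378 is essentially that number, and the slack in 380 is about 2%. The effect of loss alone is small. By formula, 5% loss costs 1 to 2 points of power (79.9% to 78.8%) and 10% costs 2 to 4 (78.9% to 76.7%), against 80.9% with no loss. These figures assume proportional hazards, the 20% and 10% risks, and loss rates that the protocol does not supply.

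Whether waiting for surgery and non-receipt lower the power further depends on what the 10% means. The document leaves that open, so it is a question for 4.4 to answer and not a shown shortfall.

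**What to change.** 1. Reconcile 6.5 with 4.4. Either remove the statement that loss was accounted for, or state the assumed loss rate in 4.4 and show how it enters the calculation.
2. In 4.4, restate the power at N = 380 for the expected loss rate, naming the method (formula or simulation) and using it throughout.
3. In 4.4, say whether the 10% is an intention-to-treat risk counted from randomisation. If it applies only to patients operated on promptly, restate the power for the expected wait and the expected share not operated on.

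The cost is protocol wording and a short recalculation. No added patients and no change to the analysis are needed. The stated power may become slightly less favourable.

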## 6.6 Follow-up of subjects withdrawn from treatment

Patients withdrawing from the study who randomized to the control arm, or prior the intervention, do not require specific follow-up. Patients withdrawing after the intervention will receive appropriate surgical care. This includes a single outpatient clinic to evaluate recovery at 6 weeks post-operative, as well as care for possible complications of surgery. After full recovery from surgery no specific follow-up is required.

Patient who refrain from surgery after randomization or cross-over from wait-and-see to surgery but do not withdraw from the study as a whole, will be followed according to the study procedures as described above and analyzed based on intention-to-treat.

## 6.7 Premature termination of the study

In case the study is ended prematurely, the investigator will notify the accredited METC, including the reasons for the premature termination.

Version number: 2, 25-04-2025

24 of 44

#### 7. SAFETY REPORTING

## 7.1 Temporary halt for reasons of subject safety

In accordance to section 10, subsection 4, of the WMO and applicable local regulations in the participating countries, the sponsor will suspend the study if there is sufficient ground that continuation of the study will jeopardise subject health or safety. The sponsor will notify the accredited METC without undue delay of a temporary halt including the reason for such an action. The study will be suspended pending a further positive decision by the accredited METC. The investigator will take care that all subjects are kept informed.

## 7.2 AEs, SAEs and SUSARs

## 7.2.1 Adverse events (AEs)

Adverse events are defined as any undesirable experience occurring to a subject during the study, whether or not considered related to the intervention. All adverse events reported spontaneously by the subject or observed by the investigator or his staff will be recorded.

Adverse events related to adhesiolysis include complications associated with abdominal surgery such as wound infection, haemorrhage, pneumonia and thrombosis. Further adhesiolysis is associated with a small risk (2-4%) of iatrogenic injury to organs such as the bowel. In case of iatrogenic bowel injury, failure of healing of this injury can results in further negative sequelae including reoperation, stoma, and ICU admission.

#### 7.2.2 Serious adverse events (SAEs)

A serious adverse event is any untoward medical occurrence or effect that

- results in death;
- is life threatening (at the time of the event);
- requires hospitalisation or prolongation of existing inpatients' hospitalisation;
- results in persistent or significant disability or incapacity;
- is a congenital anomaly or birth defect; or
- any other important medical event that did not result in any of the outcomes listed above due to medical or surgical intervention but could have been based upon appropriate judgement by the investigator.

An elective hospital admission will not be considered as a serious adverse event.

All SAEs as defined in the protocol must be reported to the Sponsor within 24 hours of the trial staff becoming aware of the event. The sponsor will report the SAEs occurring up to 3 months following treatment through the web portal *ToetsingOnline* to the accredited METC that approved the protocol [NL] and the approving ethical Commission in Belgium. SAEs that result in death or are life threatening will be reported as soon as possible after becoming aware, followed by a period of maximum of 8 days to complete the initial preliminary report. All other SAEs will be reported within a period of maximum 15 days after the sponsor has first knowledge of the serious adverse events. In Belgium all other SAEs will reported as part of the yearly progress report.

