#### 6. METHODS

## 6.1 Study parameters/endpoints

## 6.1.1 Main study parameter/endpoint

The primary outcome of the study is recurrence at 2-years of follow-up.

Recurrence is defined as a readmission for symptoms of small bowel obstruction, including lower abdominal pain, bloating and nausea with or without vomiting. In addition imaging by CT-scan should not show indications of other causes of bowel obstruction (such as an incarcerated abdominal wall hernia or tumour), which is over 90% accurate for the diagnosis of ASBO.

The incidence of recurrent ASBO increases over time. We deliberately preferred a 2-year follow-up as the primary outcome, because at this time frame it is feasible to prospectively follow-up on patients with low loss of data, and also ethically to avoid long delays in implementation of results.

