## 6.1.2 Secondary study parameters/endpoints (if applicable)

Secondary outcomes are:

- Recurrence at 5 year (identified by record linking[BE] or general practitioner data[NL])
- Recurrences needing surgery
- Recurrence risks stratified by patients and surgical characteristics (Sex, age)
- Recurrence risk in the operative subgroup stratified for laparoscopic vs open surgery
- Morbidity from elective adhesiolysis:
  - Serious adverse events and complications, graded by Clavien-Dindo score.
  - Intra-operative events (i.e. bowel injury), graded by ClassIntra®

- ICU admission
- Reinterventions within 90 days

Patient questionnaires at 1 and 2 years of follow-up

- Health-related quality of life measured by EQ5D
- Gastro-intestinal related quality of life measured by GIQLI
- Characteristics of abdominal pain
- Costs from healthcare perspective (measured by modified iMCQ)
- Costs from societal perspective (measured by modified iMCQ and iPCQ)
- Cost-effectiveness (incremental cost-effectiveness ratio, i.e. cost per QALY) Surgical follow-up
- History taking with focus on potential recurrences
  - Review of data from readmission in same hospital
  - Ask patients if there have been readmission to other hospitals
- Assessment of complaints related to obstruction
  - Chronic or recurrent nausea, bloating, abdominal pain
  - Unintended weight loss
- Physical examination focused on abdominal pain and incisional hernia

The full iMCQ and iPCQ questionnaires are quite extensive and elaborate for patients to fill out. Therefore a modified version of these questionnaires is applied, in which only the domains that are potentially affected by ASBO are included, as decided upon during an expert meeting with healthcare professionals and patient representatives. This method is frequently applied in cost-effectiveness research and also increases the number of patients completing the questionnaire.

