## 6.1.3 Other study parameters (if applicable)

At baseline we will collect data on surgical history, co-morbidity, BMI, and substance use. During the surgery we will collect data on surgical approach, intraoperative events graded by Class-Intra, extent and location of adhesions (measured by Peritoneal Adhesion Index), Completeness of adhesiolysis, and use of barrier.

At the follow-up visits we will perform history taking and physical examination focused on identification of potential readmissions for ASBO at other hospitals, chronic complaints, and late surgical complications such as incisional hernia.

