## 7.3 Follow-up of adverse events

All AEs will be followed until they have abated, or until a stable situation has been reached. Depending on the event, follow up may require additional tests or medical procedures as indicated, and/or referral to the general physician or a medical specialist. SAEs need to be reported till end of study within the Netherlands and Belgium, as defined in the protocol

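### The SAE definition exempts every elective admission, including planned treatment of late consequences of the study operation, while every confirmed recurrence counts as an SAE and mixes the safety outcome with the primary endpoint

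*Protocol*

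**What the plan says.** All from the protocol:

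- **Section 7.2.2** makes an event serious if, among other criteria, it "requires hospitalisation or prolongation of existing inpatients' hospitalisation". It then adds: "An elective hospital admission will not be considered as a serious adverse event". No condition on cause or timing is attached.
- **Section 6.1.1** defines the primary endpoint as an admission: "Recurrence is defined as a readmission for symptoms of small bowel obstruction". Nothing exempts endpoint events from the SAE definition.
- **Section 6.1.2** lists SAEs, with Clavien-Dindo-graded complications, as a secondary outcome under the morbidity of the operation. A separate item there is "Reinterventions within 90 days".
- **Section 6.1.3** has follow-up visits look for "late surgical complications such as incisional hernia". **Section 7.2.1** says of iatrogenic bowel injury that "failure of healing of this injury can results in further negative sequelae including reoperation, stoma, and ICU admission". The protocol thus recognises both hernia and stoma as possible consequences of the operation.
- **Section 2** places safety, compared with wait-and-see, in the primary objective. **Section 8** describes complications descriptively, in the operative group only.
- **On time windows**, section 7.2.2 says "The sponsor will report the SAEs occurring up to 3 months following treatment", and section 7.3 says "SAEs need to be reported till end of study within the Netherlands and Belgium".

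**The concern.** The SAE outcome is shaped by two rules that pull in different directions.

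The exemption was presumably meant to keep the trial operation itself from being reported as an SAE. As written it goes further. A hernia repair or stoma reversal is usually a planned admission some months later. Under the rule that admission is not serious, and after day 90 it is not a reintervention outcome either. It could even be Clavien-Dindo grade IIIb (intervention under general anaesthetic), the level at which section 7.4 has the DSMB review cases, and still not be an SAE through the admission.

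The hospitalisation criterion also makes every recurrence an SAE. Recurrence is the efficacy endpoint and is expected twice as often in controls. An SAE total that includes it reflects partly operative harm and partly treatment benefit, and cannot be read as either. Because safety relative to wait-and-see is part of the primary objective, readers will look for a statement about SAEs in the two arms.

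**Working it through.** **Inputs from the protocol.** Two-year recurrence 20% (control) and 10% (intervention), HR about 0.47, 80% power, two-sided alpha 0.05, 378 patients rounded up to 380, 1:1 allocation (section 4.4); organ injury risk 2–4% (section 7.2.1).

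**Inputs assumed.** An operative SAE risk *s* in the intervention arm, independent of recurrence; other SAEs equally frequent in both arms; no loss to follow-up; no operative SAEs in controls. The protocol gives no operative SAE rate, so *s* is varied.

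**1. The plan's own figure.** HR = ln(0.90)/ln(0.80) = 0.472. Schoenfeld's formula gives 56 events. At a mean event risk of (0.20 + 0.10)/2 = 0.15, N = 56/0.15 = 373.3, so 374, close to the stated 378. At 378 patients (56.7 expected events) the power is 80.7%. The recurrence rates are therefore those that underlie the design, and the sample size is not in dispute.

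**2. SAEs from recurrence alone.** With 380/2 = 190 per arm: control 0.20 × 190 = 38 patients; intervention 0.10 × 190 = 19 patients.

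**3. A between-arm count of patients with any SAE.** Intervention risk = 1 − (1 − 0.10)(1 − *s*); control risk = 0.20.

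| Assumed *s* | Intervention, any SAE | Patients of 190 | Difference from control, recurrence included | Difference, recurrence excluded |
|---|---|---|---|---|
| 2% | 11.8% | 22 | −8.2 points | +2 points |
| 4% | 13.6% | 26 | −6.4 | +4 |
| 10% | 19.0% | 36 | −1.0 | +10 |
| 11.1% | 20.0% | 38 | 0 | +11.1 |
| 15% | 23.5% | 45 | +3.5 | +15 |
| 20% | 28.0% | 53 | +8.0 | +20 |

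Break-even: 1 − 0.80/0.90 = 11.1%. Below that value the pooled count favours surgery even though surgery alone adds SAEs.

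**4. An operative-group summary.** Here the same rule acts the other way. Recurrence adds 0.10 × 190 = 19 patients to what is labelled operative morbidity. At *s* = 4%, 0.04 × 190 = 7.6 patients with operative SAEs would appear among 25.8 patients with any SAE.

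**5. Late planned admissions lost through the exemption.** The protocol gives no rate, so the number cannot be derived from it. If 1%, 2%, 5% or 10% of 190 operated patients needed such an admission (assumed), about 2, 4, 10 or 19 patients would be exempt. For scale, 2–4% organ injury is 3.8–7.6 patients, of whom only an unstated fraction would come to a stoma.

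**The case against.** Four arguments stand against a stronger version of this point.

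- **Harm data as a whole.** A reader might infer that operative harm is understated throughout the trial. The documents do not support that. Section 7.2.1 records all AEs, and section 7.3 follows them until resolved or stable. Section 6.1.2 also counts complications graded by Clavien-Dindo, with no 90-day limit on that item, as well as intra-operative events and ICU admission. Hernia is looked for at follow-up visits in both arms. The injury or reoperation behind a stoma would normally already be an SAE. What is lost is the SAE label on the late planned admission.
- **Comparison between arms.** A reader might infer that the planned SAE analysis will hide the price of surgery. No between-arm SAE analysis is fixed. Section 8 describes complications in the operative group, and there recurrences would inflate morbidity, not hide it. The masking shown above applies only if the arms are compared on a pooled SAE count.
- **Tabulation.** Recurrences are verified individually, so they can be separated later without new data, and table layout is commonly left to the SAP. This is fair for the recurrence half. It does not answer the exemption, which decides at the site what is reported as an SAE.
- **Windows.** A reader might take sections 7.2.2 and 7.3 to contradict each other. They can be read as two duties: the three-month limit governs what the sponsor forwards to the ethics committees, while reporting to the sponsor runs to the end of the study. The text does not say so, and a window that starts at treatment has no clear start for a control patient. That is unclear wording, not a demonstrated conflict.

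**Conclusion.** The point holds for the SAE outcome, not for all safety data. Two things follow directly from the text. The exemption covers planned admissions for late consequences of the study operation, and after 90 days these are outside the reintervention outcome too. And every confirmed recurrence is an SAE, so an outcome presented as operative morbidity contains the primary endpoint.

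The 38 and 19 recurrence patients rest on the plan's own rates with complete follow-up. The masking of an operative SAE risk of up to about 11% rests also on independence of operative SAEs and recurrence, on equal frequency of other SAEs, and on someone making a between-arm count. The number of exempt late admissions is known only under assumed rates. The definition should be corrected, preferably before events accrue, because it governs what sites report. The unclear reporting window is minor.

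**What to change.** In section 7.2.2:

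1. Limit the exemption to the admission for the trial adhesiolysis itself, including cross-over surgery, and to admissions planned before randomisation for a pre-existing condition.
2. State that a planned admission to treat a consequence of the study operation counts as an SAE.
3. Report SAEs by arm, with confirmed aSBO recurrences shown separately from all other SAEs. A field on the SAE form (recurrence, consequence of study surgery, other) is enough.
4. As a minor clarification in sections 7.2.2 and 7.3, state that the three-month limit concerns forwarding to the ethics committees, and that SAE collection runs from randomisation to the end of the study in both arms.

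The cost is protocol wording and one form field. The downside is a few more SAEs attributed to surgery. Sample size and primary analysis are unaffected.
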